- Compliance with Prehabilitation. Each patient will receive a prehabilitation log book in which they will record details about their home-based regimen, including the date of training, duration and intensity of exercise, IMT repetitions and threshold pressures, nutritional supplements consumed, dietary intake, and pedometer data (e.g., step counts at the beginning and end of each training session). They will be coached in the use of this log at each hospital session. Data from the logbook will be collected from patients weekly and entered into the database for analysis. In addition, because the pedometer stores 7 days of data, and the exercise physiologists will record daily step counts as a measure of overall activity at each hospital session.
- Health-Related Quality of Life will be measured with the Assessment of Quality of Life (AQoL-6D) that includes 20 items on a Guttman scale assessing 6 domains: independent living, mental health, relationships, senses, pain and coping.⁹⁷ The utility score ranges from -.04 (state worse than death) to 1.0 (full health). It is sensitive to change with a minimum clinically important difference (MCID) of 0.06.⁹⁸
- Quality of Surgical Care will be measured with the Surgical Care Survey (SCS) that includes subscales for quality of pre-surgical care (11 items), day of surgery (6 items), and postoperative care (12 items).⁹⁹
- Measures of Decision Quality include Decision Regret (5 items), Patient Centeredness of Care (12 items), Satisfaction with the Process of Decision Making (14 items), Satisfaction with the IMPACT clinic (8 items), Satisfaction with the frailty diagnosis (8 items), satisfaction with the palliative care consult (8 items), and Satisfaction with the surgeon (8 items).
- Mortality. Patients completing the 30- and 90-day surveys will be confirmed alive. For all others, chart review including telephone contact with identified surrogates will confirm vital status and date of death (if deceased).
- Length of Stay will be calculated from the date of surgery to the date of discharge or transfer from the hospital. We will also record the time spent in the intensive care unit. Intervals will be calculated in days.
- Major Complications will be abstracted from the chart according to VASQIP coding rules (Appendix). The presence or absence of each complication will be recorded separately, but analysis will focus on a dichotomous outcome indicating the occurrence of serious, Clavien-Dindo level IV complications.¹⁰⁰ These include deep wound infections, organ space infections, wound disruption, pneumonia, unplanned intubation, pulmonary embolism, mechanical ventilation for >48 hours, progressive renal insufficiency, acute renal failure, stroke, coma, cardiac arrest, myocardial infarction, bleeding in excess of 4 units, deep vein thrombosis, sepsis and *C. difficile* colitis. This approach to analyzing complications has been shown to correlate with frailty.⁶ Co-I and Chief of Surgery [name] (see letter) has authorized the VASQIP nurse abstractor to use standard VASQIP procedures to code the charts of participating patients.

Incidental Findings: If any of these tests generate an incidental finding of sufficient clinical significance to warrant review by the patient's primary care physician (PCP), we send the test results to the PCP and follow up with an encrypted email. We will also telephone the patient within a week to inform the patient of the finding and the planned PCP follow-up.

Research study methods: analysis Plan

* **Please describe the analysis plan for the study** (*it is acceptable to refer to the*

sponsor/multi-site protocol for section if applicable):

D.10. Data Analysis.

(a) General approach for quantitative data. We will first explore the data using descriptive statistics (e.g., means, standard deviations, percentiles, ranges) and graphical techniques (e.g., histograms, scatter plots) to examine key variables to assess distributional assumptions, the existence of outliers and data sparseness. For categorical variables, we will generate frequency and percentage distributions to identify data sparseness. In the event of data sparseness, categories with small frequencies will be merged when meaningful and appropriate. Continuous variables will be categorized into meaningful groups if the distributions are skewed. All analyses will be performed using Stata statistical software (StataCorp, 2013).

(b) Missing Data Strategies. We will attempt to minimize the amount of missing due to dropouts (withdrawals, lost to follow-up, or deaths) or individuals who missed at least one of the follow-up assessments (intermittent missing). In the event of missing data, we will use multiple imputation to impute the missing values.

(c) Estimate rates of recruitment, randomization, retention, and compliance with the prehabilitation intervention [Aim 1]. To assess the feasibility of recruitment, randomization, and retention, we will summarize the total number of eligible patients approached, recruited, randomized to intervention and control conditions, and retained through the completion of study procedures 90 days postoperatively, estimating rates as well as associated confidence intervals.²⁵ For those lost to follow up, we will estimate the proportion of planned in-hospital prehabilitation sessions completed before dropping out along with rates of 30-day outcome assessment (if available). For those randomized to the intervention condition, compliance with the hospital-based regimen will be measured as the number of scheduled sessions completed. If patients are able to comply with only a portion of the training regimen, this will be noted and the patient will be categorized as partially compliant. Compliance with the home-based regimen will be measured as the number of assigned activities documented in the patient logs. Overall compliance rates with confidence intervals (CIs) will be estimated for the home, hospital, and combined intervention. We will also compute rates (and CIs) of partial compliance as well as rates (and CIs) of intervention-specific task compliance.

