- (3) Estimate overall and treatment-specific summary statistics for postoperative outcomes in terms of 30- and 90-day (a) mortality, (b) major complications, (c) length of hospital stay, (d) health-related quality of life, (e) quality of surgical care, and (f) change in level of independent living.

Methods: This randomized pilot study will enroll a consecutive cohort of up to 50 Veterans identified as frail using a standardized frailty assessment and scheduled for major abdominal surgery on the general or urological surgery services at the VA Pittsburgh Healthcare System. We will randomize participants 1:1 to receive either: (1) standard preoperative optimization by the Interdisciplinary Medical Preoperative Assessment Consultation & Treatment Clinic (IMPACT), or (2) prehabilitation + standard IMPACT optimization. The 6-week long prehabilitation intervention

will include (1) strength and balance training; (2) inspiratory muscle training; and (3) nutritional coaching and supplementation. Assessments will include standard postoperative outcomes as well as the Short Physical Performance Battery to measure physical performance, Maximal Inspiratory Pressure to measure pulmonary function, and both prealbumin and the 7-point Subjective Global Assessment to measure nutrition. Outcomes will be assessed 30 or 90 days after surgery. Compliance with the prehabilitation regimen will be assessed through patient logs and pedometers. Analyses will inform the development of a larger randomized controlled trial testing the prehabilitation intervention. Findings will be relevant for the as many as 42,000 frail Veterans scheduled for major elective surgery each year.

*** Describe the study objectives. Please include primary aim and hypothesis, if applicable any secondary aims and hypotheses.**

We will examine the feasibility of a novel, multifaceted pre-habilitation intervention aimed at improving postoperative outcomes for frail Veterans undergoing major abdominal surgery. Specific aims are to:

- (1) Estimate rates of recruitment, randomization, retention, and compliance with the prehabilitation intervention;
- (2) Measure (a) physical performance, (b) pulmonary function, and (c) nutrition at baseline and 2-week intervals to estimate changes over time and explore the optimal duration of prehabilitation (2 vs. 4 vs. 6 weeks); and

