A.6. Prehabilitation is most promising among the frail. Although prehabilitation may benefit everyone, frail patients likely have the most to gain because they have the greatest deficits in physiologic reserve, and thus even modest improvements in strength, balance, and nutrition may prevent the physiologic decompensation that leads to poor outcomes.^{51,52} However, it remains unclear if frail patients can fully comply with intensive physical therapy (PT), and even if they do, it is not clear if they will build strength, muscle mass, aerobic capacity, and nutrition demonstrated in more robust populations.⁵³ A recent review demonstrates preliminary feasibility, safety and effectiveness of PT programs focused on frail populations,⁵⁴ but because the most effective interventions lasted ≥ 5 months, it remains uncertain if clinically significant benefits can be achieved in the 4-6 weeks that typically elapse between diagnosis and surgery. To begin examining these questions, researchers in Canada are conducting a multi-site RCT of prehabilitation for *cardiac* surgery.⁵⁵ *However, further research is needed to demonstrate the feasibility and effectiveness of frailty-focused prehabilitation in the non-cardiac surgery that accounts for the majority of surgery conducted in US Veteran populations.*

A.7. We therefore developed a multifaceted prehabilitation intervention for frail patients scheduled for major abdominal surgery. We will leverage the existing standard of care at VAPHS through which all patients scheduled for surgery are routinely evaluated for frailty as part of a standard preoperative risk assessment (but not risk mitigation). For those identified as frail, we will offer prehabilitation focused on increasing physiological reserve through (a) strength and balance training to support the improved outcomes associated with early mobilization after abdominal surgery,⁵⁶ (b) inspiratory muscle training to reduce postoperative pulmonary complications⁵⁷ and (c) nutritional coaching and supplementation to enhance physical performance⁵⁸ and wound healing.⁵⁹ We will also arrange occupational and physical therapy consults to identify and supply needed durable medical equipment.

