D.5. Randomization procedures and their rationale. Some patients may be reluctant to accept the possibility of randomization to control conditions, and if so, recruitment rates of a randomized trial would be diminished. We will therefore use the randomization feature in REDCap to randomize participants in a 1:1 ratio. As each patient enrolls, REDCap will assign the patient to intervention or control conditions as specified by a fixed allocation table. If patients refuse participation based on the risk of randomization, we will note this fact, but offer the opportunity to participate in the preferred arm (intervention or control). This approach will permit accurate estimates of randomization while accruing the largest possible sample size.

D.6. Prehabilitation Procedures.

(a) Overview. Prehabilitation will include hospital- and home-based components within an integrated intervention led by [name]. The hospital-based component will occur at the VAPHS Cardiac Rehabilitation facility and focus on supervised strength and balance training. One-hour sessions will be scheduled twice weekly for at least 4, but no more than 6 weeks before the operation. The home-based component will entail walking or seated pedaling on a home exerciser, as well as Respiratory Muscle Training (RMT), both of which are feasible and safe to do in a non-supervised setting. Nutritional supplementation will be linked to the composite training protocol. Compliance will be measured with exercise log books (See Appendix) and pedometers given to each participant. With the consent of the surgeon, operative dates will be scheduled to accommodate prehabilitation.

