D.7. Assessment Schedule. As shown in Table 1, research staff will collect baseline data at the time of recruitment regarding demographics, physical performance, and nutrition. We will monitor physical performance, nutrition and compliance every other week during in-hospital prehabilitation and on the day of surgery. Postoperative outcomes will be assessed 30 or 90 days after the surgery. Patient Survey Instruments will be administered either face to face, by telephone or by mail, depending on patient preference. Responses will be entered directly into REDCap using a project utility distinct from the RAI measurement tool. For patients electing surveys by mail, we will send printed copies of the Redcap forms with a self-addressed, stamped envelope for return. Responses on returned surveys will be keyed into Redcap before storing the paper surveys in locked cabinets. Instruments assessing living location, quality of life, quality of surgical care, and decision quality are described in D.8. and in the Appendix. Chart reviews will be completed by the research assistant to determine details of the surgical procedure, including postoperative mortality, length of stay, and major complications. Physical Performance Tests will be administered by the exercise physiologist in the Cardiac Rehabilitation facility, located near the IMPACT clinic, and thus convenient for patients to visit on both the days of recruitment and surgery. Nutrition assessments include serum prealbumin and Body Mass Index (BMI) collected biweekly by hospital phlebotomists, and the 7-point Subjective Global Assessment (SGA-7)²⁸ administered by hospital nutritionists at baseline and again on the day of surgery. Patient Logs will assess patient compliance with the home-based prehabilitation regimen and document progress with aerobic training, IMT and nutritional supplementation. They will be collected weekly and on the day of surgery. *Those randomized to control conditions will not complete the patient logs or the weekly in-hospital assessments, but they will complete all other assessments.*

Assessments will end after the assessment planned for 90 days after the surgery. Ideally, patients will return to the hospital for this final visit to conduct measures of physical performance and nutrition along with the survey instruments. However, if they are unable to make the visit, we will conduct the surveys over the phone.

Table 1: Assessment Schedule

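### Postoperative events are set against person-time from an undefined study start, and non-fatal harm or lost operations before surgery have no by-arm result

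*Combined protocol and SAP*

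**What the plan says.** **When outcomes are assessed.** D.7 (Assessment Schedule) says "Postoperative outcomes will be assessed 30 or 90 days after the surgery". Table 1 marks mortality at 30 and 90 days after surgery, and length of stay and major complications at 30 days only. Chart review serves "to determine details of the surgical procedure, including postoperative mortality, length of stay, and major complications". D.8 starts length of stay on the date of surgery. Aim 3 calls the whole set postoperative.

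**When the intervention acts.** Prehabilitation is delivered entirely before surgery. D.6(a): "One-hour sessions will be scheduled twice weekly for at least 4, but no more than 6 weeks before the operation". The same paragraph adds: "With the consent of the surgeon, operative dates will be scheduled to accommodate prehabilitation". The plan does not state how long controls wait.

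**Who is observed before surgery.** The two-weekly checks cover performance, nutrition and compliance. On controls, D.7 says: "Those randomized to control conditions will not complete the patient logs or the weekly in-hospital assessments, but they will complete all other assessments".

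**How events are analysed.** D.10(e) totals deaths and major complications at 30 and 90 days for all patients, overall and by arm. It divides them by person-time running from study start to the end of study, death or loss to follow-up. Study start is not defined.

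**What else bears on the point.** D.8 seeks vital status and date of death, by chart review and calls to surrogates, for anyone who does not complete the 30- and 90-day surveys. D.8 also records procedure codes for both the planned and the performed operation. D.10(c) counts retention to 90 days after surgery. D.10(b) lists deaths among the causes of dropout and applies multiple imputation to missing values, with no exception for death or for surgery that did not take place.

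**The concern.** The outcome schedule runs on a clock that starts at the operation. The rate denominator appears to run on a clock that starts earlier. Mixing the two adds preoperative days to the denominator without clearly adding preoperative events to the numerator. The arm with more preoperative days then shows the lower rate, for reasons unrelated to its outcomes.

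The preoperative period is also when the intervention is given. An unplanned admission, an emergency operation, a cancellation or a loss of operability in those weeks has no scheduled outcome and no by-arm summary. Controls have fewer study contacts before surgery, so events noticed informally would come to light more often in the trained arm. This second distortion works against the first, and the net direction cannot be predicted.

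D.10(e) says the investigators will try to assess differences between arms on these measures, and the results are meant to shape a larger trial. Whether frail patients reach their operation after prehabilitation, and when, is itself a feasibility result that trial would need.

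**Working it through.** The plan gives no figure for preoperative harm or waiting time, so there is none to reproduce. The check is how far the two clocks can move a rate.

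**Inputs**
- Up to 50 participants, allocated 1:1 (Abstract), so about 25 per arm.
- Intervention wait *w_I*: 4-6 weeks of training, 28-42 days (D.6(a)). It is measured from the start of training, so any gap after enrolment would add to it.
- Control wait *w_C*: not stated. Assumed 0, 7 or 14 days, with equal waits as the reference.
- Follow-up after surgery *f*: 30 or 90 days (Table 1).

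**Step 1. Share of intervention-arm time that is preoperative**, *w_I* / (*w_I* + *f*)
- To day 90: 28/118 = 24%; 42/132 = 32%.
- To day 30: 28/58 = 48%; 42/72 = 58%.

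**Step 2. Rate ratio, intervention/control, with identical postoperative events.** If each arm has the same number of patients and of postoperative events, and everyone is followed for the full window, the events cancel:

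ratio = (*w_C* + *f*) / (*w_I* + *f*)

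| *w_I* | *w_C* | To day 30 | To day 90 |
|---|---|---|---|
| 28 | 0 | 30/58 = 0.52 | 90/118 = 0.76 |
| 28 | 7 | 37/58 = 0.64 | 97/118 = 0.82 |
| 28 | 14 | 44/58 = 0.76 | 104/118 = 0.88 |
| 42 | 0 | 30/72 = 0.42 | 90/132 = 0.68 |
| 42 | 7 | 37/72 = 0.51 | 97/132 = 0.73 |
| 42 | 14 | 44/72 = 0.61 | 104/132 = 0.79 |
| equal | equal | 1.00 | 1.00 |

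The day-30 column assumes person-time is cut at day 30. If the 30-day count is divided by follow-up to day 90 instead, the day-90 column applies. With waits of 42 and 28 days the ratios are 0.81 and 0.89. If controls wait longer (42 against 28 days) they reverse, to 1.24 and 1.12.

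**Step 3. The same in patient-days.** Take one death per arm, 25 patients per arm, waits of 42 and 14 days, and follow-up to day 90. Person-time is 25 x 132 = 3,300 and 25 x 104 = 2,600 patient-days. The rates are 0.30 and 0.38 per 1,000 patient-days, a ratio of 0.79, although both arms have the same one death in 25.

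**Step 4. How many preoperative events could be at issue.** The risk *q* of death or no surgery before the operation is assumed. The expected number among 25 is 25*q*, and the chance of at least one is 1 - (1 - *q*)^25.

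| *q* | Expected | At least one |
|---|---|---|
| 2% | 0.5 | 40% |
| 4% | 1 | 64% |
| 8% | 2 | 88% |
| 12% | 3 | 96% |

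**Step 5. What one event does.** Exact 95% intervals for 25 patients are 0-13.7% with no events and 0.1-20.4% with one. A single event counted or left out visibly changes an arm's result, and both intervals are too wide to settle a question about harm.

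**The case against.** The strongest reply is that D.10(e) already covers deaths. It summarises them for all patients, by arm, over person-time that is not restricted to operated patients and ends at death. D.8 seeks vital status and date of death for everyone without a completed survey. On that reading a preoperative death is both recorded and counted. This largely stands. A reader might infer from Table 1 that preoperative deaths drop out and that the comparison is confined to patients who reach surgery. The documents do not support that. What remains is that Aim 3, D.7 and Table 1 call the same outcomes postoperative, so an analyst could follow either reading.

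Preoperative attrition also shows up elsewhere. Under Aim 1, an unoperated patient would appear as not retained, and comparing the planned and performed procedure codes may reveal a cancelled or changed operation. This stands in part: neither source yields a reason, a date or a planned by-arm summary.

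It may also be said that a delay confined to the intervention arm is assumed. That is correct. A.6 refers to "it remains uncertain if clinically significant benefits can be achieved in the 4-6 weeks that typically elapse between diagnosis and surgery", so the usual interval may already accommodate the course. Recruitment takes place at the preoperative clinic, which may leave less time than that, and operative dates can be moved. A longer wait in the intervention arm is therefore plausible, but it is not stated.

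Finally, D.11 says the pilot does not estimate an effect size, and Step 5 shows that it could not. A reader might infer that better counting would reveal whether postponing surgery costs lives. With about 25 per arm it would not.

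**Conclusion.** The concern holds as a mismatch of time origins together with a gap in by-arm reporting.

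- **Mismatch.** If only postoperative events are counted over time from study start, identical postoperative events give an intervention/control ratio of 0.68-0.88 to day 90 and 0.42-0.76 to day 30. These figures rest on a 28-42 day intervention wait, an assumed 0-14 day control wait, study start meaning enrolment or the start of training, and full follow-up. With equal waits there is no distortion.
- **Deaths.** Preoperative deaths would probably be recorded and may be counted, but the plan does not say so clearly.
- **Gap.** Non-fatal preoperative harm, delayed or cancelled surgery and time to surgery have no by-arm result. A patient never operated on has no defined 30- or 90-day time point.
- **Imputation.** As worded, D.10(b) would allow values to be imputed after death, or postoperative values for patients who had no operation.

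This should be corrected before analysis. Confidence is moderate: some pages and the appendices are not available, and a safety-monitoring section may lie there. Even so, Table 1 and D.10(e) would still need to be reconciled.

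**What to change.** Amend Table 1, D.10(b) and D.10(e) as follows.

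1. Define study start as randomisation, or enrolment for those who choose their arm under D.5. Count deaths and serious events from that date in every participant, operated or not, with numerator and person-time on the same clock. Also give the proportion with each event at one fixed time after that date, the same in both arms and long enough to cover the preoperative period plus 90 days (42 + 90 = 132 days at least). This avoids a rate that depends on the mix of low- and high-risk time.
2. Using the same chart review and surrogate call in both arms, record preoperative death, unplanned admission, emergency operation, cancelled or changed operation with reason, and days to surgery. Report these by arm.
3. Keep the 30- and 90-day postoperative figures as a separate set among operated patients, with follow-up counted from surgery.
4. Do not impute outcomes after death, or postoperative outcomes for patients never operated on. Report the number in each category by arm.

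The cost is a protocol amendment and slightly more abstraction time per patient, including a later vital-status check for those operated on early. The existing chart reviewer and surrogate-call procedure suffice, and no visit is added.

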(b) Hospital-based Training will be scheduled twice weekly and include strength and balance training. All sessions will begin with an assessment of the subject's vital signs and a review of their progress with home-based training. Based on evaluation of the exercise log books and pedometer data, the exercise physiologist will reinforce the goals and techniques of the home-based regimen as needed. After the assessment phase, subjects will complete 5 minutes of warm-up with low-intensity walking or seated pedaling. Seated pedaling can be used to exercise the upper extremities in cases of lower extremity disability. Mode of exercise will depend on patient preference and safety, but the same mode of exercise will be used in both the hospital- and home-based regimens (see below). Subjects will then complete 10 minutes of balance training tailored to each subject's capacities and progressing as tolerated. Regimens will uniformly include elements of static, tandem and one-foot stands, weight shifts, side steps, crossovers, grape vines, backward walking, and stepping over objects. Balance training will be coupled with an additional 10 minutes of transitional movement training to enable and strengthen the proper form of movements required after surgery such as lying-to-sitting and sitting-to-standing. Next, subjects will complete 25 minutes of strength training (2 sets with 8-12 repetitions) focused on a spectrum of antagonist muscles for the core abdominal muscles impacted by surgery, including hip flexors and extensors, obliques, rhomboids, erector spinae, and latissimus dorsi. In addition, to optimize mobility and daily function, we will target other muscle groups in the legs, arms, and hands (quads, hamstrings, calf, biceps, triceps, and hand groups). The hospital-based session will finish with full body stretching and reassessment of vital signs. During each session, the exercise physiologist will use a log book (Appendix) to

record completion of each component along with details about the duration and intensity of the aerobic training, balance, and weight training. Regimens such as this have been shown to be both safe and effective among the frail elderly,⁷⁶ and the improvements in strength and balance will likely facilitate early mobilization after surgery—an intervention shown to improve outcomes after surgery.⁵⁶

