(c) Home-based Training: Patients will be coached to complete home-based training at least 2-3 days a week and more as tolerated. Exercise will start with a 5 minute warm-up (i.e., slow paced walking or seated pedaling, consistent with the mode of exercise used in the hospital). The same exercise modality will then extend for an additional 30 minute aerobic training session. This phase will entail efforts at a comfortable speed with increasing duration. We will coach patients to reach 30 minutes of continuous, moderate exertion of 11-13 on the Borg Rating of Perceived Exertion (RPE) scale,⁷⁷ but it is expected that initially many subjects may only tolerate shorter intervals. In that case, 5-10 minute intervals of less intense (slower) walking or pedaling may then be combined with periods of rest, with the goal of repeating and elongating them as tolerated until 30 continuous minutes are achieved. If/when 30 minutes of continuous exercise is achieved (at RPE 11-13), the next step will be to progress the intensity (speed) with short periods of relatively greater speed (RPE 13-15) for 1-2 minutes, and alternate with slower intensity (speed) at RPE 11-13. Patients will record the duration and exertion of training in their log books along with step counts from their pedometer affixed to either the patient's waist (walking) or wrist/ankle (pedaling). Family members or other caregivers can assist patients in completing the log books if needed. After aerobic activity, home-based exercise will continue with 30 minutes of progressive RMT using a Threshold RMT device (Respirronics™). Threshold RMT requires that subjects inspire and exhale through a mouthpiece at a comfortable rate using diaphragmatic breathing techniques. The Threshold IMT device prohibits the subject from inhaling or exhaling until a set negative pressure is achieved and overcome. This is accomplished through the use of weighted plungers or spring-loaded valves. It is inexpensive, convenient, and easy to administer at home. We will set each patient's threshold to 40% of maximal inspiratory and expiratory pressures (MIP & MEP) as measured by the Test of Incremental Respiratory Endurance (TIRE)⁶⁰ device, a breathing assessment tool that links a pneumotachometer to a computer tablet and can be used gauge inspiratory pressures. MIP & MEP are the peak pressures generated by respiratory muscles when patients forcibly inhale or exhale against resistance. It is analogous to a maximum weight lifted in the gym but measures the strength of the diaphragm and accessory breathing muscles. MIP & MEP will be defined as the average of 3 assessment breaths on a TIRE device. MIP & MEP will be measured at the first hospital-based session and bi-weekly thereafter, adjusting the Threshold RMT device to maintain a workload at 40% of MIP & MEP as respiratory muscle conditioning improves. Patients will again record the threshold and number of breaths completed in the 30-minute session in log books. Family members or other caregivers can assist patients in completing the log books if needed. Regimens such as this have been shown to increase MIP (15 cm H₂O, 95% CI 9-21) and halve the risk of postoperative pulmonary complications following abdominal surgery (relative risk 0.48, 95% CI 0.26 to 0.8).⁷⁸

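### Home compliance is scored from patient-kept logs alone, although the protocol promises logs and pedometers and staff collect device counts that never enter the rate

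*Combined protocol and SAP*

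**What the plan says.** Two places promise two sources. The abstract (Methods) says "Compliance with the prehabilitation regimen will be assessed through patient logs and pedometers". D.6(a) says "Compliance will be measured with exercise log books (See Appendix) and pedometers given to each participant".

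Pedometer data are then collected by two routes. In D.6(c) the patient writes them down: "Patients will record the duration and exertion of training in their log books along with step counts from their pedometer". D.8 confirms that the log holds counts at the start and end of each training session and that log data go into the analysis database. D.8 also gives a staff route, using the device's 7-day memory: "the exercise physiologists will record daily step counts as a measure of overall activity at each hospital session".

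The analysis section, D.10(c), uses one source: "Compliance with the home-based regimen will be measured as the number of assigned activities documented in the patient logs". It promises rates with confidence intervals for the home, hospital and combined regimens, and for partial and task-specific compliance.

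On who keeps the log, D.6(c) and D.6(d) say "Family members or other caregivers can assist patients in completing the log books if needed". On how much home training is assigned, D.6(c) says "Patients will be coached to complete home-based training at least 2-3 days a week and more as tolerated".

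**The concern.** Section A.6 treats it as an open question whether frail patients can keep up with intensive training, and compliance is named in Aim 1. For the home component the plan collects a record that does not pass through the patient's own writing, describes it in advance as a compliance measure, and then gives it no role in the score. A log-only rate cannot show whether sessions were recorded that did not take place.

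The combined rate inherits the problem. Hospital sessions are logged by the exercise physiologist (D.6(b)), while home activities are logged by the patient. A single combined figure would mix observed and self-reported data without saying so.

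A second gap sits beside this one. D.10(c) defines a count but promises a rate, and the home target is a range with an open top. Two analysts could take the same logs and report different percentages.

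**Working it through.** No compliance figure is stated in the plan, so there is none to reproduce. The check is to trace each record and then test what the scoring rule can and cannot show.

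**1. Where each record goes**

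- Activities written in the log (D.6(c), D.8): scored in D.10(c).
- Start and end step counts copied into the log by the patient (D.6(c), D.8): in the database, but not independent of the person reporting the session. D.10(c) does not say that an entry needs them to count.
- Stored daily totals read by staff (D.8): independent of the log, described there as a measure of general activity, and not mentioned in D.10(c).
- Review of log and pedometer at the start of each hospital session (D.6(b)): used to reinforce the home regimen. Nothing says that it corrects or confirms the score.

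No section says how device data enter the rate, what counts as agreement, or what happens when log and device differ.

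**2. What over-recording would do to the rate (assumed inputs)**

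Let T be the true share of assigned activities done, and o the share of missed activities logged as done. Then

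logged rate = T + (1 − T) × o

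- T = 0.60: o = 0.10 gives 0.60 + 0.40 × 0.10 = 0.64; o = 0.20 gives 0.68; o = 0.30 gives 0.72; o = 0.50 gives 0.80.
- T = 0.80: o = 0.10 gives 0.80 + 0.20 × 0.10 = 0.82; o = 0.50 gives 0.90.

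Both T and o are assumptions; the documents give neither. The confidence interval that D.10(c) promises covers sampling error only, so it would sit around the logged rate and give no sign of the shift. I have not attached an interval to these figures, because D.10(c) counts activities and sets no threshold for calling a patient compliant.

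**3. The denominator**

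Inputs: 2 or 3 days a week (D.6(c)); 4 to 6 weeks of training (D.6(a)). The minimum number of home days is days × weeks:

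- 4 weeks: 2 × 4 = 8, or 3 × 4 = 12.
- 6 weeks: 2 × 6 = 12, or 3 × 6 = 18.

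A patient with 12 logged sessions in 6 weeks scores 12/12 = 100% on the lower target and 12/18 = 67% on the higher one.

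**4. What a device check can do**

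Take the rule that a logged session is device-consistent if its start-to-end step count is present and does not exceed the staff-recorded total for that date.

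- An entry with no step count fails.
- An entry claiming more steps than the device stored that day fails.
- An invented entry small enough to fit within that day's ordinary walking passes.

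So failure shows a discrepancy, but passing does not prove that a session took place. The check reaches only walking and pedaling. It cannot reach respiratory training, diet or supplements.

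**The case against.** The strongest reply is that log and device are not really separate. The log that D.10(c) scores already carries step counts for each session, and staff look at log and pedometer together at every hospital visit. That stands in part: a reader might infer that the home data are wholly unchecked, and the documents do not support this. They also do not say that caregivers keep the log, only that they may help. What remains is that the copied counts come from the same hand as the session entries, and that the staff review has no stated effect on the score.

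Second, a reader might infer that this is the central rate of Aim 1. It is not. Aim 1 also covers recruitment, randomization, retention and hospital compliance, and D.11 bases the planning of the next study on recruitment and retention. Only the home and combined compliance rates are affected. Nor is this a bias between arms, since controls keep no logs (D.7).

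Third, a daily total cannot confirm a 30-minute session, and pedaling may be under-counted. Both points stand. They are why the device-checked rate should be read as a consistency check, split by exercise mode, and set beside the log-based rate without replacing it.

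Fourth, a reader might infer from the open-ended home target that extra days in good weeks can offset missed weeks. D.10(c) counts assigned activities and does not say that days above the minimum are assigned, so the text does not establish this. The log form in the Appendix, which is not in the text reviewed here, may list the assigned items; if so, D.10(c) should cite it. The choice between 2 and 3 days as the denominator still needs to be stated.

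**Conclusion.** The mismatch is real and rests on the text alone: compliance is to be measured with logs and pedometers, staff collect independent step counts, and the only scoring rule for home compliance leaves those counts out. The home rate and the combined rate therefore cannot reveal over-recording.

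The documents do not show that over-recording will occur, or how much. The shift from 60% to between 64% and 72% holds only under the assumed 10% to 30% of missed activities logged as done. A reader might infer that the compliance rate will be inflated; the supportable statement is that inflation could not be detected.

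The denominator gap needs no such assumption: the same 12 sessions in 6 weeks score 100% or 67%, depending on which end of the stated range is used.

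This is a worthwhile, low-cost correction to an Aim 1 rule. It does not undermine the pilot.

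**What to change.** In D.10(c):

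- Keep the log-based home rate. Beside it report, with confidence intervals, a device-checked rate for the home aerobic component only.
- Count a logged session as device-consistent when its start-to-end step count is present and does not exceed the staff-recorded stored total for that date. Class dates with no stored data as unconfirmed and report how many there are.
- Show results separately for walking and pedaling.
- Label respiratory training and nutrition compliance as self-reported, and say that the combined rate mixes staff-recorded and self-reported parts.
- State one weekly denominator for the home rate, chosen by the sponsor and reconciled with the range in D.6(c).

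If pedometers are not meant to contribute to compliance, reword the abstract and D.6(a) instead, so that the sections agree.

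The cost is analysis-plan wording and a merge, by patient and date, of data already being collected. There are two small downsides. Pedaling may be under-counted, which would lower the device-checked rate for those patients. And because the device keeps only 7 days, a longer gap between hospital sessions leaves unconfirmed dates, so patients who miss hospital sessions may have more of them.
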